- Tanner stage is performed at Baseline Visit and annually thereafter. No need to be repeated after the subject has reached Tanner Stage 5.
- Uveitis Exam by an ophthalmologist (or qualified equivalent per local practice) is performed at Screening (if no exam is done within past 6 months), then annually thereafter, and at End of study/Early Termination Visit. If the exam was performed within the past 6 months the next uveitis exam should occur 1 year after the previous exam and annually thereafter. The window for this particular examination is ± 30 days relative to the visits where uveitis exam is performed (see Section 6.2 and Section 6.2.5 for additional details). At all other visits the investigator should assess if there are potential changes in uveitis status and refer for formal evaluation if deemed clinically necessary. For JIA subtypes that may require more frequent uveitis examination, investigators should manage this type of examination according to local standard of care. For subjects with sJIA, this exam is not required but if available, documentation of previous uveitis assessment(s) by an ophthalmologist (or qualified equivalent per local practice) should be reviewed, the date of the prior examination recorded, and the presence/absence of active uveitis documented.
- Serious adverse events (SAEs) are captured from the time of informed consent at Screening. For more information see Section 7.2.5. Adverse events (AEs) are captured following the first dose of investigational product.
- The contraception check is an opportunity to confirm that contraception is used consistently and correctly. Also, it is the opportunity to assess changing potential to father/bear children and allows for implementing contraception and pregnancy testing as children mature physically and behaviorally during conduct of the study.

TABLE OF CONTENTS

PROTOCOL SUMMARY	7
SCHEDULE OF ACTIVITIES.....	11
LIST OF TABLES	21
LIST OF FIGURES	21
APPENDICES	22
1. INTRODUCTION	23
1.1. Indication.....	23
1.2. Background	23
1.2.1. Study Rationale.....	23
1.2.2. Dose Rationale.....	24
1.2.3. Single Reference Safety Document	26
2. STUDY OBJECTIVES AND ENDPOINTS.....	26
2.1. Objectives.....	26
2.1.1. Primary	26
2.1.2. Secondary	26
2.1.3. Exploratory	26
2.2. Endpoints.....	27
2.2.1. Primary	27
2.2.2. Secondary	27
2.2.3. Exploratory	28
2.3. Benefit/Risk Assessment.....	28
2.3.1. Risk Assessment	28
2.3.2. Benefit Assessment.....	29
2.3.3. Overall Benefit/Risk Conclusion.....	30

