7.2.8. Assessment of Pubertal Development

Determination of physical and sexual maturation will be performed annually at study visits using the Tanner stages by a trained physician/clinician in the presence of a parent/legal guardian or clinic staff member, until the subject has reached Tanner Stage 5.

In the event the parent/legal guardian or child 9 years or older refuses the examination for sexual maturity, or if not possible per site practice or local regulations, subject self-assessment of Tanner staging that uses photographs or line drawings corresponding to the Tanner stages will be offered to obtain information on pubertal status while avoiding intrusiveness.

Based on a multi-informant investigation, Dorn et al. (1990)⁹ and Taylor et al. (2001)¹⁰ found that when boys and girls were shown schematic drawings (5 ordinal-scaled drawings/photographs corresponding to the Tanner stages), their self-ratings correlated quite well with health-care-provider examination Tanner staging.

The Tanner stage rating will be assigned by the clinician/physician based on the exam or based on the subject self-report. If the clinician believes the subject's self-report may reflect an earlier or later pubertal stage than the clinician believes is correct, the clinician will review

the self-report form with the subject and/or parent/legal guardian to clarify the subject's responses. This review will be done in the presence of another person, either the parent/legal guardian or a clinic staff member. At the end of the review, the clinician will then assign a best estimate Tanner stage rating.

Note that pubertal development in the U.S. begins as early as age 8 and completes as late as age 17. Once a subject has reached the highest stage of development (Stage 5) then that score may be carried forward for the remainder of the study.

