## 5.3. Methods to Manage Missing Data

Missing data will not be imputed, and all analyses will be based on available data except Tanner Stage assessment and missing joint assessment. For Tanner Stage assessment, once a subject has reached the highest stage of development (Stage 5) then that score will be carried forward for the remainder of the study. More specifically, any missing Tanner Stage assessment after a Stage 5 score will be “imputed” with Stage 5, up to the next non-missing Tanner Stage assessment prior to study discontinuation. For missing joint assessment, the imputation method is provided in [Appendix 1.2](#)

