## 6. ANALYSES AND SUMMARIES

### 6.1. Primary Endpoints

The primary endpoints are standard laboratory safety data, adverse event (AE) reports, body weight, height and tanner stages. The Safety Analysis Set (SAS) will be used for analysis. For some endpoints, e.g., overall AE summary and AEs by SOC and PT, analyses will also be performed in sJIA2 analysis set and any additional summaries will be detailed in the programming plan.

All the safety data, including the following, will be summarized descriptively through appropriate data tabulations, descriptive statistics, and graphical presentations by visit:

- Adverse events will be summarized according to Pfizer standards.
- Safety laboratory tests will be summarized according to Pfizer standards.
- Subjects meeting certain cutoffs will be summarized for the following parameters: neutrophil counts, lymphocyte counts, serum creatinine levels, liver tests, lipid levels, hemoglobin.
- Subjects meeting discontinuation and monitoring criteria (see Protocol Appendix 8) will be summarized.
- Serious infections will be summarized.
- Incidence rate will be calculated for AEs of special interest. See Section [6.6](#) for details.
- For pubertal development as measured by Tanner Stage, a shift table of Tanner Stages from baseline to each post-baseline visit will be constructed by age group (2 to <6 years, 6 to <12 years, and 12 years or older) for males and females separately. The percentages in the shift table will be based on the number of subjects with available tanner stage data at both baseline and the post-baseline visit of interest.

- For assessment of growth as measured by body weight and height, a table of descriptive statistics for body weight and height standardized Z-scores (actual values and changes from baseline) at each visit will be constructed by age group (2 to <6 years, 6 to <12 years, and 12 years or older) for males and females separately.

Height (weight) Z-score is calculated using the following formulation:

$$Z = \frac{(X/M)^L - 1}{LS}, L \neq 0$$

Or

$$Z = \ln(X/M) / S, L = 0$$

where X is the physical measurement (e.g., height, weight) and L, M, and S are the values from standardized growth charts provided by the US Centers for Disease Control website (<http://www.cdc.gov/GrowthCharts/>) by gender for children from birth to 240 months. The Z-score cannot be calculated if age >240 months.

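### The Tanner shift table keeps children recorded at Stage 5 but drops unassessed children below it, so any missed assessments would overstate the share at Stage 5

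*Protocol*

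**What the plan says.** Pubertal development by Tanner stage is among the primary endpoints in SAP 3.1. The protocol schedules it annually and at the End of Study/Early Termination Visit, and the Schedule of Activities adds "No need to be repeated after the subject has reached Tanner Stage 5". Protocol 7.2.8 says of a child at Stage 5 "then that score may be carried forward for the remainder of the study".

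SAP 5.3 sets the general rule: "Missing data will not be imputed, and all analyses will be based on available data except Tanner Stage assessment and missing joint assessment". The Tanner exception is narrow: "any missing Tanner Stage assessment after a Stage 5 score will be “imputed” with Stage 5". This fill stops as soon as another actual stage is recorded, and it does not extend past discontinuation. Nothing is filled for a missed assessment at Stages 1 to 4.

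SAP 6.1 plans a shift table from baseline to each visit, by three age groups and by sex. Of its denominator it says: "The percentages in the shift table will be based on the number of subjects with available tanner stage data at both baseline". The same sentence requires data at the later visit as well. The SAP plans neither a count of children not assessed nor a sensitivity analysis for this table.

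**The concern.** Two children are in the study at the same annual visit and neither has a Tanner assessment in the window. The one already recorded at Stage 5 is counted, as Stage 5. The one last recorded at Stage 4 is left out. Inclusion thus depends on the outcome being tabulated, and the losses fall on children not yet recorded as mature.

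For a drug given through puberty the natural safety question is delay. A table that tends to lose children below Stage 5 leans towards reassurance, and without counts a reader cannot tell maturation from missing assessments.

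Some missed assessments are foreseeable. Protocol 7.2.8 provides for refusal ("In the event the parent/legal guardian or child 9 years or older refuses the examination for sexual maturity") by offering self-assessment, and Tanner staging is not on the list of items that must be done at a telehealth visit in Appendix 14.

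**Working it through.** The documents state no Tanner proportion and no missing rate, so there is no plan figure to reproduce. What follows shows size under stated assumptions.

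**Inputs.** From the SAP: Stage 5 is carried forward once recorded; other missing stages are not filled; the denominator is children with data at baseline and at the visit. Assumed: children start at Stage 4, 40% reach Stage 5 each year, nobody leaves the study, and a fraction r of children not yet recorded at Stage 5 is assessed at each annual visit, independently of current stage.

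**Formulas** for annual visit k, with T(0) = K(0) = 0:
- True share at Stage 5: T(k) = T(k−1) + 0.4 × [1 − T(k−1)]
- Share recorded at Stage 5: K(k) = K(k−1) + r × [T(k) − K(k−1)]
- Share the table shows below Stage 5: r[1 − T(k)] / {r[1 − T(k)] + K(k)}

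**Month 12.** 0.6r / (0.6r + 0.4r) = 60%, the true value, for any r. There is no bias at the first annual visit.

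**Month 36.** T = 0.784, so 21.6% are truly below Stage 5.

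| Missed | K at Months 12, 24, 36 | Shown below Stage 5 | Gap from 21.6% |
|---|---|---|---|
| 0% | 0.400, 0.640, 0.784 | 21.6% | 0 |
| 10% | 0.360, 0.612, 0.7668 | 0.1944/0.9612 = 20.2% | 1.4 points |
| 20% | 0.320, 0.576, 0.7424 | 0.1728/0.9152 = 18.9% | 2.7 points |
| 40% | 0.240, 0.480, 0.6624 | 0.1296/0.7920 = 16.4% | 5.2 points |

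At 20% missed, the gap over years 1 to 5 is 0, 2.7, 2.7, 2.0 and 1.4 points.

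**No carry-forward at all.** With complete data and no re-examination after Stage 5, each visit would show only new arrivals: [T(k) − T(k−1)] / {[T(k) − T(k−1)] + 1 − T(k)} = 40% at every visit, against a true 78.4% at Month 36. That is far worse than the planned rule.

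**Opposite direction.** Take one visit with a true Stage 5 share of 50%, of which 5 points were reached during the index study and never recorded here. The table shows 0.45 / (0.45 + 0.50r): 47.4% with nothing missed and 50.0% with 10% missed.

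**What bounds would give**, Stage 4 row, Month 36, 20% missed. Assessed below Stage 5: 17.3%. Recorded at Stage 5: 74.2%. Not assessed: 8.5%. Of the 0.216 × 0.2 = 4.3% who were missed while still at Stage 4, a fraction 0.48 / (1 − 0.12) = 0.545 is seen at Stage 4 again later and can be filled, which adds 2.4 points. Counting the rest as advanced gives 17.3 + 2.4 = 19.6% below Stage 5 (from unrounded terms). Setting them to the last recorded stage gives 100 − 74.2 = 25.8%. The true 21.6% lies between.

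**The case against.** The strongest reply is that the plan limits missed assessments. SAP Appendix 1.12 gives Tanner its own contiguous windows, a year or more wide (Days 2–547 for Month 12, Days 548–912 for Month 24), so a late assessment still counts. The End of Study/Early Termination Visit includes Tanner staging (Protocol 6.2.5). Refusal leads to an offer of self-assessment, which also yields a stage. The telehealth list is a minimum, and Appendix 14 asks sites to follow the schedule where possible and allows home visits. All of this stands, and it makes 40% missing hard to defend. It does not remove the asymmetry or show how much is missing.

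Several stronger readings are tempting, and the documents do not support them:
- A reader might infer that the table is bound to overstate maturity. It does so only if children below Stage 5 who are still in the study go unassessed.
- Pooling all baseline stages gives a larger figure. With 40% at Stage 5 at baseline, 60% at Month 12 and 20% missed, the share shown below Stage 5 is (0.40 × 0.8) / (0.40 + 0.60 × 0.8) = 36.4%, against a true 40%. That gap comes wholly from children already at Stage 5 at baseline, whom a shift table shows as a separate baseline category.
- A reader might expect steady growth with time. In percentage points the gap in the Stage 4 row rises and then falls.
- Ordinary dropout does not create the effect, because the carry-forward ends at discontinuation. A child who reaches Stage 5 but was never recorded there is dropped too.

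It can also be said that an all-in-study denominator alone makes the displayed share below Stage 5 worse: 0.40 × 0.8 = 32% in the pooled example. This is right, and the fix has to respect it. Finally, the study is descriptive with no hypotheses (SAP 5.1), so no decision rule is affected.

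**Conclusion.** The point holds in a conditional form. SAP 5.3 and 6.1 together make inclusion in a primary-endpoint percentage depend on the outcome, and missed assessments below Stage 5 push the displayed Stage 5 share up. The size is modest: zero with complete data, zero at the first annual visit for rows below Stage 5, and about 1.4 points (10% missed) to 2.7 points (20% missed) in the Stage 4 row at Month 36. This rests on an assumed 40% yearly advance, assumed missing rates, and missingness unrelated to current stage. The effect would sit mainly in the group aged 12 or older; strata with no Stage 5 child are unaffected.

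The net direction is not certain. For enrolment gaps of 14 days or less, baseline is the index-study baseline (SAP 3.4.1), and no Tanner assessment is scheduled at entry to this study. The SAP does not say how a Stage 5 first reached during the index study is treated. If it is left missing, maturity is understated.

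The Stage 5 carry-forward is not the fault. The gap is the available-data denominator for Stages 1 to 4.

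**What to change.** Keep the Stage 5 carry-forward and amend SAP 5.3 and 6.1 as follows:
- By visit and within each baseline stage, show the numbers in study, assessed, carried forward and not assessed. Use all children still in the study with a baseline Tanner stage as the denominator.
- Fill a missed stage when the recorded stages before and after it are equal.
- For the remaining missed assessments report two bounds: set to the last recorded stage (least mature) and counted as advanced (most mature). Define how far a child below Stage 4 is taken to advance.
- Do not present the all-in-study percentage below Stage 5 on its own as the estimate.
- State how a Stage 5 first recorded during the index study is handled.

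No new data collection is needed in this study. The cost is SAP wording, minor programming, and a table in which missing assessments are visible.

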1. INTRODUCTION

1.1. Indication

Tofacitinib (also known as CP-690,550) is currently approved in the United States and more than 98 countries for the treatment of adult patients with moderately to severely active rheumatoid arthritis (RA) who have had an inadequate response or intolerance to methotrexate. In adults, it is also approved for the treatment of psoriatic arthritis (PsA), ulcerative colitis and ankylosing spondylitis. It may be used in combination with methotrexate or other non biologic disease modifying antirheumatic drugs (DMARDs). In the pediatric population, from 2 to less than 18 years of age, tofacitinib is approved for active polyarticular course JIA in the United States and polyarticular JIA and juvenile PsA in the EU.

1.2. Background

Tofacitinib is a potent, selective inhibitor of the JAK family of kinases with a high degree of selectivity against other kinases in the human genome. In kinase assays tofacitinib, inhibits JAK1, JAK2, JAK3, to a lesser extent TyK2. In cellular settings where JAK kinases signal in pairs, tofacitinib preferentially inhibits signaling by heterodimeric receptors associated with JAK3 and/or JAK1 with functional selectivity over receptors that signal via pairs of JAK2. Inhibition of JAK1 and JAK3 by tofacitinib blocks signaling through the common gamma chain containing receptors for several cytokines, including interleukins (IL) IL-2, -4, -7, -9, -15 and -21.^{1,2,3} These cytokines are integral to lymphocyte activation, proliferation, and function and inhibition of their signaling may thus result in modulation of multiple aspects of the immune response. In addition, inhibition of JAK1 will result in attenuation of signaling by additional pro-inflammatory cytokines, such as IL-6 and IFN γ . At higher exposures, inhibition of erythropoietin signaling could occur via inhibition of JAK2 signaling.

1.2.1. Study Rationale

The tofacitinib pediatric development program is designed to demonstrate both efficacy, as demonstrated by a reduction in signs and symptoms of JIA in subjects 2 years of age and older, and safety supporting the use of tofacitinib for the treatment of pediatric subjects with JIA.

The rationale of this study is to enable subjects potentially benefitting from treatment in a previous qualifying/index study to continue to receive tofacitinib at the same dose as the qualifying/index study (unless further analysis of the qualifying/index study data indicate otherwise), and to characterize long-term safety and tolerability of tofacitinib for the treatment of JIA.

It is anticipated that benefit of continued treatment with tofacitinib for individual subjects in this study will have been established in the qualifying/index study as per the Investigator's assessment. Potential risks of continued treatment are expected to be consistent with those described in the Single Reference Safety Document (current version of the tofacitinib Investigator Brochure).

1.2.2. Dose Rationale

Selection of the 5 mg BID dose of tofacitinib for this long term extension (LTE) study of tofacitinib in JIA subjects is supported by pharmacokinetic (PK) data from the completed Phase 1 PK study of tofacitinib in JIA subjects (A3921103) and the benefit/risk profile of tofacitinib in adult RA subjects.

Tofacitinib clearance is not dependent on body weight for weights >40 kg based on tofacitinib PK in the adult RA population [body weight range of the population studied was 40 kg-140 kg]. Thus the dose of tofacitinib in adolescents with body weight ≥40 kg was set to 5 mg twice a day (BID), the only approved dose of tofacitinib in adult RA subjects in most countries. The doses for JIA subjects with lighter weight were selected to match the predicted steady state concentrations ($C_{avg,ss}$) in JIA subjects with body weight ≥40 kg after administration of a 5 mg BID dose.

Generally, for approved DMARDs in the treatment of JIA, partial extrapolation of efficacy from the adults to pediatrics is well accepted (Dunne et al, Pediatrics 2011).¹¹ Thus, the dose range selected for JIA subjects across the weight-group is predicted to achieve $C_{avg,ss}$ values equivalent to efficacious doses in adult RA population (between 3 to 5 mg BID dose).

Due to lack of prior PK data for tofacitinib in the pediatric population, initial doses for the PK study (A3921103) were selected using allometric (weight-based) scaling of the adult PK parameters with an exponent of 0.75 (θ in Eq. 1 and 2). For most small molecules, the relationship between clearance (CL) and body weight (BWT) is best described by a non-linear relationship; whereby clearance is commonly scaled to the 0.75 power of BWT and volume of distribution (V) is linearly correlated with BWT. Following these principles, with $C_{avg,ss}$ as the target, CL and dose were allometrically scaled and the exponent estimated (Eq. 1 and Eq. 2, respectively), assuming bioavailability (F) to be similar between adults and children. These relationships were used to obtain pediatric doses that were expected to provide similar $C_{avg,ss}$ to adult RA tofacitinib 5 mg BID dosing (assuming 70 kg BWT for an adults).

$$CL(ped)/F = CL(adult)/F \times \left(\frac{BWT}{70}\right)^{\theta} \quad \text{Eq. 1}$$

$$Dose(ped) = Dose(adult) \times \left(\frac{BWT}{70}\right)^{\theta} \quad \text{Eq. 2}$$

The PK study of tofacitinib in subjects with JIA has completed. A total of 26 subjects between 2 and 17 years of age and weighing between 13.9 and 70.9 kg were dosed with 2 to 5 mg BID doses of tofacitinib for 5 days in Study A3921103. Pharmacokinetic evaluations were performed on Day 5 at pre-dose, 0.5, 1, 2, 4 and 8 hours. Non-compartmental analysis (NCA) was performed on the PK profiles, and a summary of PK parameters is presented in [Table 1](#).

Table 1. Summary of Tofacitinib Pharmacokinetic Parameter Values (CV%) in JIA Subjects from Study A3921103

Cohort	No. Subjects	Weight (Kg)	AUC _{tau} (ng·hr/mL)	C _{max} (ng/mL)	T _{max} (hr)	T _{1/2} (hr)	CL/F (L/hr)
Cohort 1 12 to <18 yrs	8	38.3-70.9	156.6 (25)	46.97 (40)	0.75 [0.5-6.9]	2.616 ± 0.454	28.09 (22)
Cohort 2 6 to <12 yrs	9	20.3-48.9	118.8 (27)	41.67 (29)	1.0 [0.50-2.05]	1.949 ± 0.294	25.48 (40)
Cohort 3 2 to <6 yrs	9	13.9-19.8	142.5 (32)	66.15 (28)	0.50 (0.50-1.92)	1.771 ± 0.406	20.53 (33)

*Geometric Mean (CV%) for Area under the effect curve (AUC_{tau}), C_{max}, apparent clearance (CL/F) and arithmetic mean (±SD) for terminal half-life (T_{1/2}); Median [range] for Time to C_{max} (T_{max}); Source: Table 14.1.2.1.1, date of table generation: 18 January 2016 (08:42) and Table 14.4.3.1.1, date of table generation: 02 February 2016 (05:22).

The exposures from the first 16 subjects in Cohort 1 and Cohort 2 in Study A3921103 (as shown above) indicated higher CL/F values than predicted from Eq. 1 using an allometric component of 0.75 and thus resulting AUC_{tau,ss} and C_{max,ss} values 38-53% and 19-28% lower, respectively, as compared to adult RA subjects (252 ng·hr/mL and 58 ng/mL respectively; data on file). However, due to higher doses administered in Cohort 3 (protocol was amended based on interim analysis of PK data from Cohorts 1 and 2 to target systemic exposure equivalent to 5 mg BID in adult rheumatoid arthritis [RA] subjects), AUC_{tau} in Cohort 3 was comparable to Cohort 1 and higher than Cohort 2, and C_{max} value was higher than both preceding cohorts.

A population PK model was developed, and concentrations from the 26 JIA subjects enrolled in study A3921103 were fitted adequately using an one compartment model with first-order absorption (K_a) and linear elimination. In this model, body weight was used as an allometric covariate to describe changes in CL/F and V/F with changes in weight and the exponents being estimated. The estimated power exponents were 0.292 (%RSE: 40.1%) for CL/F and 0.843 (%RSE: 12.3%) for V/F. Similar to adult RA subjects, age, gender and race were not found to be significant covariates to describe inter-subject variability in tofacitinib CL/F or V/F. Formulation (solution or tablets) was tested as a covariate for first order absorption constant, K_a, and was found to be not statistically significant. Thus it was not included in the final model.

Following model fitting, Monte Carlo simulations using the estimated population PK parameters and their inter individual variability were conducted to evaluate doses expected to provide $C_{avg,ss}$ and $C_{max,ss}$ concentrations comparable to efficacious concentrations in adult RA subjects with maximum nominal dose capped at 5 mg BID. With the current proposed dosing regimen ([Section 5.1](#)), the predicted $C_{avg,ss}$ is similar to that of 3-5 mg BID in adult RA subjects across the expected weight range, with $C_{max,ss}$ not exceeding that of 10 mg BID in most subjects. Based on the results of the modeling using allometric scaling and the PK data from Study A3921103, it is expected that doses of 2 to 5 mg BID (depending on body weight of the subjects), administered approximately 12 hours apart will provide safe and efficacious exposures of tofacitinib in this study (see [Section 5.1](#) for the planned doses and regimens).

PK collection time points (see [Section 7.4.1](#)) in this study were decided based on optimal PK sampling design utilizing the population PK (POPPK) model built on data from A3921103.

